**Table 2: Treatments Administered**

Study Treatment	Dose Level	Frequency of Administration and Duration of Treatment	Route of Administration	Infusion Time, minutes
Relatlimab a	160 mg, 80 mg	Q4W Until progression, unacceptable toxicity, withdrawal of consent, or CR	IV	██████
Nivolumab a	480 mg	Q4W Until progression, unacceptable toxicity, withdrawal of consent, or CR	IV	██████

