### **STUDY ASSESSMENTS AND ANALYSES:**

#### **Safety Analyses:**

Safety assessments will be based on reported AEs and the measurement results of vital signs, ECGs, physical examinations, and clinical laboratory tests. AEs will be coded using the most current version of Medical Dictionary for Regulatory Activities and the incidence of observed AEs will be tabulated and reviewed for potential significance and clinical importance.

[REDACTED]

[REDACTED] Both AEs and laboratory tests will be graded using the National Cancer Institute Common Terminology Criteria for Adverse Events v5.0.

[REDACTED]

[REDACTED]

[REDACTED]

[REDACTED]

[REDACTED]

[REDACTED]

[REDACTED]

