### **3.2.6      *Relatlimab Combined with Nivolumab Clinical Activity***

[REDACTED]

[figure not shown]
More recently, CA224047, a global, double-blind, randomized, Phase 2/3 study comparing relatlimab plus nivolumab in a fixed-dose combination (FDC) formulation (relatlimab [RELA] 160 mg + nivolumab 480 mg Q4W [RELA + NIVO FDC]) to nivolumab 480 mg Q4W in participants with previously untreated advanced melanoma, demonstrated a statistically significant and clinically meaningful benefit by dual inhibition of the LAG-3 and PD-1 pathways. The study achieved its primary endpoint, demonstrating statistically significant improvement in PFS by blinded independent clinical review (BICR) with RELA + NIVO FDC compared to nivolumab monotherapy in all randomized subjects (N = 714) (PFS hazard ratio = 0.75 [95% CI: 0.62, 0.92], P-value = 0.0055). With a median follow-up of 13.2 months, the median PFS in the RELA + NIVO FDC group was 10.1 months (95% CI, 6.4–15.7) compared to 4.6 months (95% CI, 3.4–5.6) in the nivolumab monotherapy arm. PFS rates at 12 months were 47.7% (95% CI, 41.8–53.2) and 36.0% (95% CI, 30.5–41.6) for RELA + NIVO FDC and NIVO, respectively. The PFS benefit of RELA + NIVO FDC were consistent across key prespecified subgroups. Follow up for the secondary endpoints of OS and ORR is ongoing.

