### **3.2.7 Nivolumab Combined with BMS-986205 Clinical Activity**

### 3.2.8 Relatlimab Combined with Nivolumab Clinical Safety

Refer to the IB Table 5.5.1-1 for details of the dose levels and DLTs for participants treated in the Part B (combination therapy escalation).

Source:

[Redacted text]

More information can be found in the relatlimab IB.

The safety profile of the combination of RELA + NIVO FDC (N = 355) was confirmed in the pivotal Phase 2/3 global, multicenter study, CA224047, in previously untreated advanced melanoma participants. The study findings demonstrated a well-tolerated regimen with a manageable safety profile and without unexpected safety signals. The incidence of Grade 3-4 drug-related AEs was 18.9% in the RELA + NIVO FDC group versus 9.7% in the nivolumab monotherapy group. There were 3 treatment-related deaths with RELA + NIVO FDC and 2 with nivolumab-treated participants. Drug-related AEs (any grade) led to treatment discontinuation in 14.6% and 6.7% of participants in the RELA + NIVO FDC and nivolumab monotherapy groups, respectively.

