**Table 4-1: Objectives and Endpoints**

Objectives	Endpoints
Primary	

 
Part 1A and Part 1B: To determine the safety, tolerability, DLTs, and MTD of relatlimab administered in combination with nivolumab and BMS-986205 or nivolumab and ipilimumab in participants with advanced malignant tumors.
 
	
 
Incidence of clinical laboratory test abnormalities, AEs, SAEs, AEs meeting protocol-defined DLT criteria, AEs leading to discontinuation, and deaths.
 

 
Part 2A and Part 2B: To investigate safety and tolerability of relatlimab triple combinations in distinct cohorts of participants with advanced malignant tumors.
 
	
 
Incidence of clinical laboratory test abnormalities, AEs, SAEs, AEs leading to discontinuation, and deaths.
 

 
To investigate the antitumor activity of relatlimab triple combinations in participants with advanced malignant tumors.
 
	
 
ORR, DCR, and mDOR in participants with advanced malignant tumors.
 

Secondary	

 
To investigate the antitumor activity of relatlimab triple combinations in participants with advanced malignant tumors.
 
	
 
mPFS and PFSR at 6 and 12 months in participants with advanced malignant tumors.
 

Exploratory	

Abbreviations: AE = adverse event; DCR = disease control rate; DLT = dose-limiting toxicity; IgG = immunoglobulin G; [REDACTED]; mDOR = median duration of response; [REDACTED]; mPFS = median progression-free survival; MTD = maximum tolerated dose; ORR = overall response rate; [REDACTED]; PFSR = progression-free survival rate; [REDACTED]; SAE = serious adverse event; [REDACTED]

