## 5.4 Scientific Rationale for Study Design

Despite innovations in cancer treatment, alternative therapies are needed for participants with advanced cancer. The emerging role of combination immune-modulating therapies in producing deep and durable responses in a variety of tumor types, as well as early clinical data from trials studying relatlimab in combination with nivolumab, the combination of an IDO1 inhibitor with pembrolizumab, and the combination of nivolumab and ipilimumab, suggest that there may be a potential benefit with a triple combination that targets multiple mechanisms in action.

Overall, the safety profile of relatlimab in combination with nivolumab has been manageable, and there were no additional toxicities with relatlimab in combination with nivolumab. Similarly, the safety profile of BMS-986205 has been manageable both as monotherapy and in combination with nivolumab. Therefore, it is expected that the addition of relatlimab to nivolumab and BMS-986205 (in doses already shown to be safe in combination with nivolumab) or to nivolumab and ipilimumab backbone regimens (with known tolerability in specific tumor types) will be safe. The incidence of IMAEs will continue to be monitored across both triple combinations as participants are treated in the study in order to assess the impact of relatlimab on the known toxicity of nivolumab monotherapy and nivolumab combination regimens. The benefit-risk ratio supports evaluation of these triple combinations in participants with advanced cancer.

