## 10.3 Statistical Analyses

Final analysis will be performed after all participants are enrolled and have been followed for the minimum time to evaluate the primary endpoint. The statistical analysis plan will be developed and finalized before the database lock for the final analysis. A description of the participant population will be included in the statistical output reported, including subgroup of age, gender, and race. Below is a summary of planned statistical analyses of the primary and secondary endpoints. In general, summaries will be performed by dose level, cohort, and indication. If sufficient data are not available such that adequate interpretation of the result is not warranted, some summaries may not be performed and only listings will be presented.

[REDACTED]

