**Table 10.3.2-1: Overview of Safety Analysis Methods**

Endpoint	Statistical Analysis Methods
Incidence of AEs, SAEs, AEs meeting protocol-defined DLT criteria, AEs leading to discontinuation and deaths AEs will be graded according to CTCAE v5.0	DLT rate by dose level; frequency distribution of treated participants with AE using the worst CTC grade. Participants will only be counted (1) once at the PT level, (2) once at the SOC level, and (3) once in the “total participant” row at their worst CTC grade, regardless of SOC or PT.
Incidence of clinical laboratory test abnormalities Laboratory values will be graded according to CTCAE v5.0	Laboratory shift table using the worst CTC grade on treatment per participant.

Abbreviations: AE = adverse event; CTC = Common Terminology Criteria; CTCAE = Common Terminology Criteria for Adverse Events; DLT = dose-limiting toxicity; PT = preferred term; SAE = serious adverse event; SOC = system organ class.

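### Outside the Part 1 DLT rate, the visible safety analyses are crude worst-grade proportions, so summaries set side by side mix toxicity with length of exposure

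*Combined protocol and SAP*

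**What the plan says.** - The Part 2 primary safety endpoint in Table 4-1 is "Incidence of clinical laboratory test abnormalities, AEs, SAEs, AEs leading to discontinuation, and deaths". Part 1 adds AEs that meet the DLT criteria. No time frame is visible in either row.
- Table 10.3.2-1 analyses AEs as a "frequency distribution of treated participants with AE using the worst CTC grade", each participant counted once per level, and laboratory tests as a shift to the worst on-treatment grade. Section 10.3.2 makes the treated population the denominator.
- The Safety Analyses text in the Protocol Summary says that "the incidence of observed AEs will be tabulated and reviewed for potential significance and clinical importance". Further text there is redacted.
- Treatment continues "Until progression, unacceptable toxicity, withdrawal of consent, or CR" (Table 2 of the Protocol Summary, repeated in Table 7.1-1). Under Tables 2-2 and 2-3, non-serious AEs are collected from first dose until a redacted time after discontinuation.
- Section 10.3: "In general, summaries will be performed by dose level, cohort, and indication".
- Section 5.4 says that immune-mediated AEs will be monitored "in order to assess the impact of relatlimab on the known toxicity of nivolumab monotherapy and nivolumab combination regimens".
- The exception is the DLT rate by dose level. Section 7.4.6 counts DLTs in an interval that starts on the first day of treatment.

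**The concern.** The proportion of participants who ever have an event depends on how often events occur and on how long people are watched. Here the second part varies with outcome: those who progress early leave treatment early, and those who benefit stay. The expansion cohorts cover different tumours and both IO-naive and IO-progressed participants (Section 3.1.1), so time on treatment may well differ between the groups that Section 10.3 tabulates. At the same toxicity per month, a group that progresses early would look better tolerated than one that benefits for longer. The same distortion enters when these percentages are set against nivolumab regimens studied elsewhere, which is what Section 5.4 has in mind. The plan handles unequal follow-up for PFS and duration of response with Kaplan-Meier methods, but the visible text has nothing comparable for the safety endpoints, which are also primary.

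**Working it through.** The plan states no safety figure to reproduce, so this checks the mechanism only.

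**Inputs.** Section 3.2.6, for the randomised melanoma study: "the median PFS in the RELA + NIVO FDC group was 10.1 months", against 4.6 months with nivolumab alone. Section 3.2.8: "The incidence of Grade 3-4 drug-related AEs was 18.9% in the RELA + NIVO FDC group versus 9.7% in the nivolumab monotherapy group". Assumptions: time on treatment is exponential with these medians, and the AE hazard h is the same in both groups.

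**Constant hazard.** With μ = ln 2 / median, μ = 0.1507 per month (4.6 months) and 0.0686 (10.1 months). The probability of an event on treatment is P = h/(h + μ). Setting P = 9.7% at 4.6 months gives h = 0.1507 × 0.097/0.903 = 0.0162 per month. The same h at 10.1 months gives 0.0162/(0.0162 + 0.0686) = 19.1%. The ratio is 19.1/9.7 = 2.0.

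**With a post-treatment collection window of f months** (length redacted; 1 and 3.3 months assumed), P = 1 − [μ/(h + μ)]·exp(−hf). Recalibrated to 9.7%, the longer-exposed group shows 18.0% (f = 1) or 16.2% (f = 3.3), ratios of 1.9 and 1.7.

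**Risk only in the first T months**, P = [h/(h + μ)]·[1 − exp(−(h + μ)T)], again recalibrated to 9.7%:

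| T (months) | h per month | 4.6-month group | 10.1-month group | Ratio |
|---|---|---|---|---|
| 2 | 0.0594 | 9.7% | 10.5% | 1.08 |
| 3 | 0.0426 | 9.7% | 10.9% | 1.12 |
| 6 | 0.0262 | 9.7% | 12.0% | 1.24 |

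**How the two remedies behave under the same model.**

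*Cumulative incidence at a fixed time t*, with end of risk as a competing event, is [h/(h + μ)]·[1 − exp(−(h + μ)t)]. With the constant hazard (week 8 = 1.84 months, week 24 = 5.52, week 48 = 11.04):
- week 8: 2.6% vs 2.8%, ratio 1.08
- week 24: 5.8% vs 7.1%, ratio 1.22
- week 48: 8.2% vs 11.6%, ratio 1.42

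The artefact is small early and grows with time.

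*First events per person-time.* With a constant hazard this is 1.62 per 100 person-months in both groups, so the ratio is 1. With front-loaded risk, expected time at risk is [1 − exp(−(h + μ)T)]/(h + μ) + exp(−(h + μ)T)/μ:
- T = 2: 0.0970/5.99 vs 0.1048/13.04, or 1.62 vs 0.80 per 100 person-months, ratio 0.50
- T = 6: 0.0970/5.99 vs 0.1200/12.82, or 1.62 vs 0.94, ratio 0.58

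Long event-free exposure dilutes the rate, and the bias reverses. Neither summary is safe alone.

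**The case against.** - **The main dose-level comparison is protected.** The Part 1 DLT rate runs from first dose. This stands, so not every primary safety endpoint is affected. AE collection also runs past the end of treatment; only the laboratory table is limited to time on treatment.
- **No formal safety comparison is planned.** Table 4-1 asks for a description of safety and tolerability, for which crude incidence is an ordinary answer. The relatlimab phrase in Section 5.4 is a purpose of monitoring, not an objective. This stands and lowers the weight of the point. It does not remove it, because the plan still sets groups side by side and looks outward to known toxicity.
- **Exposure adjustment would not isolate what relatlimab adds.** A reader might infer that crude percentages are why that question cannot be answered. The documents do not support this: both regimens contain relatlimab (Section 5.1), so there is no concurrent group without it. Adjustment makes the external comparison fairer and no more.
- **The near-match of 19.1% to the quoted 18.9% proves nothing.** A reader might infer that the excess in the melanoma study was only longer exposure. The match follows from the assumptions. PFS is not time on treatment: Section 8.1 allows for treatment beyond progression, and drug-related AEs stopped treatment in 14.6% vs 6.7% (Section 3.2.8).
- **Efficacy does not by itself set the direction of AE percentages.** In the RCC dose-regimen study in Section 3.2.5, two groups with the same ORR of 40.4% had Grade 3-4 rates of 38.3% and 61.7%. True differences in toxicity can outweigh exposure.
- **The separate SAP may already cover this.** Section 10.3 calls its content a summary and leaves the SAP for later. That SAP was not available for this review, so absence is claimed for the visible text only.

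**Conclusion.** The point holds in a limited form, as a cheap improvement. Outside the Part 1 DLT rate, the visible AE and laboratory analyses are crude worst-grade proportions over a follow-up that depends on time on treatment. Side-by-side and external readings therefore mix toxicity with exposure. On the illustration, a 4.6 vs 10.1 month difference produces a spurious ratio of about 1.1 if risk falls in the first 2 to 3 months, 1.2 if it is spread over 6 months, and 2.0 if the hazard is constant. In percentage points, that is roughly 1 to 9 on a base of 9.7%. These figures rest on PFS standing in for time on treatment, exponential durations and an identical hazard in both groups. They show what crude percentages cannot distinguish; they are not an estimate of bias in this trial or a re-analysis of the cited one.

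**What to change.** Keep the crude tables and label them descriptive. Add to Table 10.3.2-1, and carry into the SAP, by dose level, cohort and regimen:

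1. duration of exposure;
2. cumulative incidence at fixed times from first dose, for example weeks 8 and 24, by the Aalen-Johansen method with death and end of the AE risk period as competing events;
3. first events per 100 person-months at risk.

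Apply items 2 and 3 to drug-related Grade 3-5 AEs, SAEs, AEs leading to discontinuation and immune-mediated AEs, which Section 9.2.2 already has investigators identify. Report items 2 and 3 together and rank neither first: item 2 keeps some dependence on exposure at later times, and item 3 is diluted by long exposure when risk is front-loaded. In Section 5.4, state that any contribution of relatlimab is a descriptive external comparison, since every participant receives it.

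The cost is wording and a few extra tables from dates already collected. The design does not change, and Section 10.3 leaves room to do this before the final database lock.

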#### **Efficacy Assessments:**

Disease assessment with computed tomography and/or magnetic resonance imaging, as appropriate, will be performed at baseline, and the date of the first dose, and then periodically [REDACTED]

[REDACTED]

Disease assessments at other time points may be performed as clinically indicated. [REDACTED]

[REDACTED]

[REDACTED] Sites will be trained prior to scanning the first study participant. Image acquisition guidelines and submission process will be outlined in the CA224048 Imaging Manual to be provided by [REDACTED]

[REDACTED]

[REDACTED] Changes in tumor measurements will be assessed by the Investigator and tumor responses will be determined using RECIST v1.1 criteria.

**Data Monitoring Committee:** No

## 2 SCHEDULE OF ACTIVITIES

**Table 2-1: Screening Procedural Outline for All Study Parts (CA224048)**

Procedure	Screening Visit -28 days	Day -14 to Day -1 Visit	Notes a
Eligibility Assessments			
Informed Consent	X		A participant is considered enrolled only when a protocol-specific informed consent is signed. Obtain participant's number from interactive response technology (IRT). For Protocol Amendment 05, all current participants will be re-consented. New participants will sign the updated informed consent for Protocol Amendment 05.
IRT Participant Assignment	X		After the participants meet all eligibility criteria, sites will use IRT for participant number assignment. Subsequent visits will be registered into the IRT system for drug supply (see Section 7.2 ). If the IRT system is not available, participants will be enrolled manually.
Inclusion/Exclusion Criteria	X		See Section 6.1 and Section 6.2 .
Medical History	X		
Performance Status	X		Eastern Cooperative Oncology Group (ECOG) Performance Status (see Appendix 6 ).
Prior Systemic Therapies	X		Includes prior cancer treatment regimens and medications administered within 4 weeks (28 days) of study dose administration.
	X		

**Table 2-1: Screening Procedural Outline for All Study Parts (CA224048)**

Procedure	Screening Visit -28 days	Day -14 to Day -1 Visit	Notes a
Concomitant Medications	X		Collected during the 4 weeks (28 days) prior to Cycle 1 Day 1.
Safety Assessments			
Physical Examination (PE)	X		If PE screening is performed within 24 hours prior to dose administration on Day 1, a single examination may count as both the screening and predose evaluation.
Physical Measurements	X		Includes height and weight.
Vital Signs		X	Includes body temperature, seated blood pressure, and heart rate. Blood pressure and heart rate should be measured after the participant has been seated quietly for at least 5 minutes.
Oxygen Saturation	X		Collected at rest via pulse oximetry to establish baseline. .
Chest Radiograph	X		Posterior-anterior and lateral chest x-ray to establish baseline.
Laboratory Tests			
Laboratory Tests		X	
	X		
		X	

**Table 2-1: Screening Procedural Outline for All Study Parts (CA224048)**

Procedure	Screening Visit -28 days	Day -14 to Day -1 Visit	Notes a
Urinalysis		X	See Section 9.4.4.
Thyroid Function Tests		X	See Section 9.4.4.
Genetic Mutation Status	X		[REDACTED]
Serology	X		See Section 9.4.4. Viral testing to be completed within 28 days prior to treatment assignment. For human immunodeficiency virus (HIV); testing at sites where locally mandated. [REDACTED]
Pregnancy Test (Women of Childbearing Potential [WOCBP] Only)	X		Women of childbearing potential (WOCBP) only. Sample tested at screening and within 24 hours prior to dose administration. The serum pregnancy test may be completed on the first day of treatment, provided the results are available before the start of study drug.
Follicle Stimulating Hormone (FSH)	X		Women only, as needed to document postmenopausal status. Females under the age of 55 years must have a serum FSH level > 40 mIU/mL to confirm menopause.

**Table 2-1: Screening Procedural Outline for All Study Parts (CA224048)**

Procedure	Screening Visit -28 days	Day -14 to Day -1 Visit	Notes a
Adverse Event Reporting			
Monitor for Serious Adverse Events (SAEs)	X		All SAEs must be collected from the date of participant's written consent until [REDACTED] after discontinuation of dose administration or participation in the study if the last scheduled visit occurs at a later time. [REDACTED] Electronic SAEs (eSAEs) should be approved in the BMS Electronic Data Capture (EDC) tool within 5 business days of entry.
Clinical Complaints		X	Collected during the 2 weeks prior to Cycle 1 Day 1.
Tumor Assessments/Baseline Efficacy Assessments			
Body Imaging	X		See Section 9.1 ; must be performed within 28 days prior to first dose.
Brain Imaging	X		Magnetic resonance imaging (MRI) of the brain without and with contrast is required for participants with known or suspected brain metastases who have not had brain imaging within [REDACTED] of anticipated first study drug administration. See imaging assessment details in Section 9.1 .
Other Imaging: Bone Scan	X		See Section 9.1 ; as clinically indicated per local standards.

Abbreviations: AE = adverse events; [REDACTED]; CRF = case report form; [REDACTED]; ECOG = Eastern Cooperative Oncology Group; EDC = electronic data capture; [REDACTED]; eSAEs = electronic serious adverse events; FSH = follicle stimulating hormone; G6PD = glucose-6-phosphate dehydrogenase; HIV = human immunodeficiency virus; IgG = immunoglobulin; IRT = interactive response technology; [REDACTED]; MRI = magnetic resonance imaging; [REDACTED]; PE = physical examination; [REDACTED]; SAE = serious adverse events; [REDACTED]; WOCBP = women of childbearing potential.

a Some of the assessments referred to in this section may not be captured as data in the case report form (CRF). They are intended to be used as safety monitoring by the treating physician. Additional testing or assessments may be performed as clinically necessary or where required by institutional or local regulations.

**Table 2-2: On-treatment Procedural Outline Part 1A (Relatlimab + Nivolumab + BMS-986205) and Part 1B (Relatlimab + Nivolumab + Ipilimumab)**

Procedure	Cycle 1 [REDACTED]					Cycle 2+[REDACTED]						Notes e,f
	[REDACTED] (± 2 days)	[REDACTED] (± 2 days)	[REDACTED] (± 2 days)	[REDACTED] (± 2 days)	[REDACTED]	[REDACTED] (± 2 days)	[REDACTED] (± 2 days)	[REDACTED] (± 2 days)	[REDACTED] (± 2 days)	[REDACTED]	End of Treatment (EOT) a,b,c	
Safety Assessments												
Physical Examination (PE)	X					X					X	Predose.
Symptom-directed PE		X	X	X				X				Predose. [REDACTED]
Performance Status	X	X	X	X		X		X			X	Eastern Cooperative Oncology Group (ECOG) Performance Status for all participants (see Appendix 6 ). [REDACTED]

**Table 2-2: On-treatment Procedural Outline Part 1A (Relatlimab + Nivolumab + BMS-986205) and Part 1B (Relatlimab + Nivolumab + Ipilimumab)**

Procedure	Cycle 1 [REDACTED]					Cycle 2+ [REDACTED]					End of Treatment (EOT) a,b,c	Notes e,f
	[REDACTED] (± 2 days)	[REDACTED] (± 2 days)	[REDACTED] (± 2 days)	[REDACTED] (± 2 days)	[REDACTED]	[REDACTED] (± 2 days)	[REDACTED] (± 2 days)	[REDACTED] (± 2 days)	[REDACTED] (± 2 days)	[REDACTED]		
Vital Signs	X See notes.	X	X	X		X		X			X	Includes temperature, seated blood pressure (BP), and heart rate (HR). BP and HR should be measured after the participant has been seated quietly for at least 5 minutes. On Cycle 1 Day 1 , vital signs will be obtained prior to the infusion [REDACTED] [REDACTED] Vital signs on subsequent treatment visits will be collected prior to the first infusion [REDACTED] [REDACTED] If any vital sign is abnormal (based upon clinician assessment) at the final check, the participants must be observed further for a period of time, as clinically indicated. [REDACTED]
Oxygen Saturation	X	X	X	X		X		X			X	Collected at rest via pulse oximetry. Oxygen levels will be used in combination with clinical signs and symptoms and radiographic images to evaluate pulmonary/respiratory status. Changes in O 2 levels will not be used in isolation to document or diagnose pulmonary toxicity. [REDACTED]

**Table 2-2: On-treatment Procedural Outline Part 1A (Relatlimab + Nivolumab + BMS-986205) and Part 1B (Relatlimab + Nivolumab + Ipilimumab)**

Procedure	Cycle 1 [REDACTED]					Cycle 2+ [REDACTED]					End of Treatment (EOT) a,b,c	Notes e,f
	[REDACTED] (± 2 days)	[REDACTED] (± 2 days)	[REDACTED] (± 2 days)	[REDACTED] (± 2 days)	[REDACTED]	[REDACTED] (± 2 days)	[REDACTED] (± 2 days)	[REDACTED] (± 2 days)	[REDACTED] (± 2 days)	[REDACTED]		
[REDACTED]	X	X	X	X		X					X	[REDACTED]
Chest Radiograph	See notes.											As clinically indicated.
Laboratory Tests d	X	X	X	X		X		X			X	On-study laboratory tests (including hematology, serum chemistry, endocrine panel, troponin, [REDACTED] urinalysis, and pregnancy testing) to be done on site/locally. Laboratory tests may be collected within 3 days prior to dose administration. [REDACTED]

**Table 2-2: On-treatment Procedural Outline Part 1A (Relatlimab + Nivolumab + BMS-986205) and Part 1B (Relatlimab + Nivolumab + Ipilimumab)**

Procedure	Cycle 1 [REDACTED]					Cycle 2+ [REDACTED]					End of Treatment (EOT) a,b,c	Notes e,f
	[REDACTED] (± 2 days)	[REDACTED] (± 2 days)	[REDACTED] (± 2 days)	[REDACTED] (± 2 days)	[REDACTED]	[REDACTED] (± 2 days)	[REDACTED] (± 2 days)	[REDACTED] (± 2 days)	[REDACTED] (± 2 days)	[REDACTED]		
[REDACTED]	See Notes											[REDACTED]  For C1D1, value taken at screening (pre-treatment assignment) may be used and need not be repeated. See Section 9.4.4 for laboratory test requirements.
Clinical Observation d	See Notes											All participants should be evaluated for any immune-mediated adverse events. Evaluations should occur every week (± 1 day) up to and including Week 8. Participants with any clinical symptoms should immediately be evaluated. For non-dosing visits, assessments may be performed remotely by the Investigator/delegate.
Part 1A Only (BMS-986205 treated) Methemoglobin	X	X	X	X		X		X			X	Predose, [REDACTED], and additional assessments as clinically indicated (see Section 9.4.4 ). [REDACTED]

**Table 2-2: On-treatment Procedural Outline Part 1A (Relatlimab + Nivolumab + BMS-986205) and Part 1B (Relatlimab + Nivolumab + Ipilimumab)**

Procedure	Cycle 1 [REDACTED]					Cycle 2+ [REDACTED]					End of Treatment (EOT) a,b,c	Notes e,f
	[REDACTED] (± 2 days)	[REDACTED] (± 2 days)	[REDACTED] (± 2 days)	[REDACTED] (± 2 days)	[REDACTED]	[REDACTED] (± 2 days)	[REDACTED] (± 2 days)	[REDACTED] (± 2 days)	[REDACTED] (± 2 days)	[REDACTED]		
Pregnancy Test (Women of Childbearing Potential [WOCBP])	X		X			X		X			X	A pregnancy test must be performed within 24 hours prior to administration of intravenous study drug. Serum or urine pregnancy test may be performed (for urine pregnancy test, minimum sensitivity 25 IU/L or equivalent units of human chorionic gonadotropin [hCG] is required). If results are positive, hold all study drug and perform confirmatory testing. If pregnancy is confirmed, permanently discontinue all study drug and immediately notify Sponsor per Section 9.2.6 .
Assess Adequate Contraceptive Use	X		X			X		X				For WOCBP and male participants who are sexually active with WOCBP, assess for continued use of acceptable methods of contraception (see Appendix 4 ).
Adverse Event Reporting and Concomitant Medication Assessments												
Concomitant Medication Assessments	Continuously											Review prior to dose administration.
Monitor for Non-serious Adverse Events (AEs)	X											Non-serious AEs will be collected starting with the first dose of study drug and through [REDACTED] after discontinuation of treatment. See Section 9.2 : Adverse Events.

**Table 2-2: On-treatment Procedural Outline Part 1A (Relatlimab + Nivolumab + BMS-986205) and Part 1B (Relatlimab + Nivolumab + Ipilimumab)**

Procedure	Cycle 1 [REDACTED]					Cycle 2+ [REDACTED]					End of Treatment (EOT) a,b,c	Notes e,f
	[REDACTED] (± 2 days)	[REDACTED] (± 2 days)	[REDACTED] (± 2 days)	[REDACTED] (± 2 days)	[REDACTED]	[REDACTED] (± 2 days)	[REDACTED] (± 2 days)	[REDACTED] (± 2 days)	[REDACTED] (± 2 days)	[REDACTED]		
Monitor for Serious Adverse Events (SAEs)						X						All SAEs must be collected from the date of participant's written consent until [REDACTED] post discontinuation of treatment or participation in the study if the last scheduled visit occurs at a later time. eSAEs should be approved in the BMS Electronic Data Capture (EDC) tool within 5 business days of entry. See Section 9.2: Adverse Events .
Sample Collection												
[REDACTED]												[REDACTED]
[REDACTED]												[REDACTED]
[REDACTED]												[REDACTED]
[REDACTED]												[REDACTED]

**Table 2-2: On-treatment Procedural Outline Part 1A (Relatlimab + Nivolumab + BMS-986205) and Part 1B (Relatlimab + Nivolumab + Ipilimumab)**

Procedure	Cycle 1 [REDACTED]					Cycle 2+ [REDACTED]						Notes e,f
	[REDACTED] (± 2 days)	[REDACTED] (± 2 days)	[REDACTED] (± 2 days)	[REDACTED] (± 2 days)	[REDACTED]	[REDACTED] (± 2 days)	[REDACTED] (± 2 days)	[REDACTED] (± 2 days)	[REDACTED] (± 2 days)	[REDACTED]	End of Treatment (EOT) a,b,c	
Additional Research Sampling	X											Residual samples will be used for additional research. See Section 9.8.3 .
[REDACTED]												
[REDACTED]												
[REDACTED]												
[REDACTED]												
[REDACTED]												
[REDACTED]												
[REDACTED]												
[REDACTED]												
[REDACTED]												
[REDACTED]												
[REDACTED]												
[REDACTED]												
[REDACTED]												
[REDACTED]												
[REDACTED]												
[REDACTED]												
[REDACTED]												
[REDACTED]												
[REDACTED]												
[REDACTED]												
[REDACTED]												
[REDACTED]												
[REDACTED]												
[REDACTED]												
[REDACTED]												
[REDACTED]												
[REDACTED]												
[REDACTED]												
[REDACTED]												
[REDACTED]												
[REDACTED]												
[REDACTED]												
[REDACTED]												
[REDACTED]												
[REDACTED]												
[REDACTED]												
[REDACTED]												
[REDACTED]												
[REDACTED]												
[REDACTED]												
[REDACTED]												
[REDACTED]												
[REDACTED]												
[REDACTED]												
[REDACTED]												
[REDACTED]												
[REDACTED]												
[REDACTED]												
[REDACTED]												
[REDACTED]												
[REDACTED]												
[REDACTED]												
[REDACTED]												
[REDACTED]												
[REDACTED]												
[REDACTED]												
[REDACTED]												
[REDACTED]												
[REDACTED]												
[REDACTED]												
[REDACTED]												
[REDACTED]												
[REDACTED]												
[REDACTED]												
[REDACTED]												
[REDACTED]												
[REDACTED]												
[REDACTED]												
[REDACTED]												
[REDACTED]												
[REDACTED]												
[REDACTED]												
[REDACTED]												
[REDACTED]												
[REDACTED]												
[REDACTED]												
[REDACTED]												
[REDACTED]												
[REDACTED]												
[REDACTED]												
[REDACTED]												
[REDACTED]												
[REDACTED]												
[REDACTED]												
[REDACTED]												
[REDACTED]												
[REDACTED]												
[REDACTED]												
[REDACTED]												
[REDACTED]												
[REDACTED]												
[REDACTED]												
[REDACTED]												
[REDACTED]												
[REDACTED]												
[REDACTED]												
[REDACTED]												
[REDACTED]												
[REDACTED]												
[REDACTED]												
[REDACTED]												
[REDACTED]												
[REDACTED]												
[REDACTED]												
[REDACTED]												
[REDACTED]												
[REDACTED]												
[REDACTED]												
[REDACTED]												
[REDACTED]												
[REDACTED]												
[REDACTED]												
[REDACTED]												
[REDACTED]												
[REDACTED]												
[REDACTED]												
[REDACTED]												
[REDACTED]												
[REDACTED]												
[REDACTED]												
[REDACTED]												
[REDACTED]												
[REDACTED]												
[REDACTED]												
[REDACTED]												
[REDACTED]												
[REDACTED]												
[REDACTED]												
[REDACTED]												
[REDACTED]												
[REDACTED]												
[REDACTED]												
[REDACTED]												
[REDACTED]												
[REDACTED]												
[REDACTED]												
[REDACTED]												
[REDACTED]												
[REDACTED]												
[REDACTED]												
[REDACTED]												
[REDACTED]												
[REDACTED]												
[REDACTED]												
[REDACTED]												
[REDACTED]												
[REDACTED]												
[REDACTED]												
[REDACTED]												
[REDACTED]												
[REDACTED]												
[REDACTED]												
[REDACTED]												
[REDACTED]												
[REDACTED]												
[REDACTED]												
[REDACTED]												
[REDACTED]												
[REDACTED]												
[REDACTED]												
[REDACTED]												
[REDACTED]												
[REDACTED]												
[REDACTED]												
[REDACTED]												
[REDACTED]												
[REDACTED]												
[REDACTED]												
[REDACTED]												
[REDACTED]												
[REDACTED]												
[REDACTED]												
[REDACTED]												
[REDACTED]												
[REDACTED]												
[REDACTED]												
[REDACTED]												
[REDACTED]												
[REDACTED]												
[REDACTED]												
[REDACTED]												
[REDACTED]												
[REDACTED]												
[REDACTED]												
[REDACTED]												
[REDACTED]												
[REDACTED]												
[REDACTED]												
[REDACTED]												
[REDACTED]												
[REDACTED]												
[REDACTED]												
[REDACTED]												
[REDACTED]												
[REDACTED]												
[REDACTED]												
[REDACTED]												
[REDACTED]												
[REDACTED]												
[REDACTED]												
[REDACTED]												
[REDACTED]												
[REDACTED]												
[REDACTED]												
[REDACTED]												
[REDACTED]												
[REDACTED]												
[REDACTED]												
[REDACTED]												
[REDACTED]												
[REDACTED]												
[REDACTED]												
[REDACTED]												
[REDACTED]												
[REDACTED]												
[REDACTED]												
[REDACTED]												
[REDACTED]												
[REDACTED]												
[REDACTED]												
[REDACTED]												
[REDACTED]												
[REDACTED]												
[REDACTED]												
[REDACTED]												
[REDACTED]												
[REDACTED]												
[REDACTED]												
[REDACTED]												
[REDACTED]												
[REDACTED]												
[REDACTED]												
[REDACTED]												
[REDACTED]												
[REDACTED]												
[REDACTED]												
[REDACTED]												
[REDACTED]												
[REDACTED]												
[REDACTED]												
[REDACTED]												
[REDACTED]												
[REDACTED]												
[REDACTED]												
[REDACTED]												
[REDACTED]												
[REDACTED]												
[REDACTED]												
[REDACTED]												
[REDACTED]												
[REDACTED]												
[REDACTED]												
[REDACTED]												
[REDACTED]												
[REDACTED]												
[REDACTED]												
[REDACTED]												
[REDACTED]												
[REDACTED]												
[REDACTED]												
[REDACTED]												
[REDACTED]												
[REDACTED]												
[REDACTED]												
[REDACTED]												
[REDACTED]												
[REDACTED]												
[REDACTED]												
[REDACTED]												
[REDACTED]												
[REDACTED]												
[REDACTED]												
[REDACTED]												
[REDACTED]												
[REDACTED]												
[REDACTED]												
[REDACTED]												
[REDACTED]												
[REDACTED]												
[REDACTED]												
[REDACTED]												
[REDACTED]												
[REDACTED]												
[REDACTED]												
[REDACTED]												
[REDACTED]												
[REDACTED]												
[REDACTED]												
[REDACTED]												
[REDACTED]												
[REDACTED]												
[REDACTED]												
[REDACTED]												
[REDACTED]												
[REDACTED]												
[REDACTED]												
[REDACTED]												
[REDACTED]												
[REDACTED]												
[REDACTED]												
[REDACTED]												
[REDACTED]												
[REDACTED]												
[REDACTED]												
[REDACTED]												
[REDACTED]												
[REDACTED]												
[REDACTED]												
